4.3 Randomisation and Blinding

Randomization will be applied using an internet based Interactive Web Response Systems (IWRS). In the trial, randomization will be done using random permuted blocks (based on procedure outlined in Pocock SJ. Clinical Trials: A Practical Approach. Wiley, Chichester, 1983), stratified by site, with 1:1 allocation ratio using a randomization list. At randomization, inclusion and exclusion criteria will be verified, and confirmation of informed consent signature will be done.

While investigator and subject will not be blinded to treatment group, all cMR analyses that provide value for the endpoint will be performed by a core laboratory which will be blinded to all clinical data including treatment group.

4.4 Study Variables

Observations and records of important variables will be assessed according to the following schedule along with acceptable time-windows. Measurements outside scheduled assessment times will be considered protocol deviations.

Notable evaluations include the following:

COPY

For Control subjects:

Procedure/ Interval	Baseline / Enrollment	Immediately prior to reperfusion (PCI)Post-PCI	Catheter Removal	Discharge*	Follow-Up @ 4-6 Days	Follow-Up @ 30 Days (±7 days)	Follow-Up @ 12 months (±14 days)	Unscheduled Visit
Trial Eligibility & Informed Consent	upon arrival to hospital							
Physical Exam and Medical History	X			X				
Catheter Insertion Time	X							
Catheter Removal Time			X					
Temperature Documented	X							
Vital Signs	X							
Blood Studies RBC's, WBC's, Hct, Hgb, Platelets, Neutrophils, Eosinophils	X							
Pro BNP							X	
Lab Studies BUN, Creatinine, Na, K, Ca, Mg, Cl, P, lactic acid, glucose, amylase, lipase	X							
Any Medication Use	X	X	X	X	X	X	X	X
Troponin I or T	Collect at Baseline	Collected only if peak reached	Collected only if peak reached					
12 lead ECG	X							
Adverse Events		X	X	X	X	X	X	X
Cardiac Magnetic Resonance (cMR)					X			
NYHA Assessment							X	X
KCCQ Assessment							X	X

COPY

For Test subjects:

Procedure/ Interval	Baseline / Enrollment	Initiation of Cooling	Immediately prior to reperfusion (PCI)	Maintenance of Target Temp 32 ±1°C	Rewarming to 36°C	Catheter Removal	Discharge	Follow-Up @ 4-6 Days	Follow-Up @ 30 Days (±7 days)	Follow-Up @ 12 months (±14 days)	Unscheduled Visit
Trial Eligibility & Informed Consent	upon arrival to hospital										
Physical Exam and Medical History	X						X				
Anti-Shivering Protocol	X			X ^o							
Cold Saline Infusion		X									
Catheter Insertion Time		X									
Catheter Removal Time						X					
Temperature Documented	X	X	X	every 30 min during 3 hr cooling							
Temperature Data Download						X					
Vital Signs	X	X	X	every 30 min							
Blood Studies RBC's, WBC's, Hct, Hgb, Platelets, Neutrophils, Eosinophils	X			upon reaching target temperature	upon reaching normothermia						
Pro BNP										X	
Lab Studies BUN, Creatinine, Na, K, Ca, Mg, Cl, P, lactic acid, glucose, amylase, lipase	X										
Any Medication Use	X	X	X	X	X	X	X	X	X	X	
Troponin I or T	X	Collected only if peak reached	Collected only if peak reached	Collected only if peak reached	upon reaching normothermia, Collected only if peak reached	Collected only if Peak reached					
12 lead ECG	X										
Adverse Events		X	X	X	X	X	X	X	X	X	
Catheter Access Site Assessment						X	X	X			
Cardiac Magnetic Resonance (cMR) imaging								X			
NYHA Assessment									X	X	
KCCQ Assessment									X	X	

COPY

5 Sample Size

Sample size considerations are based on both the primary effectiveness analysis.

The primary effectiveness analyses is designed to detect a relative reduction of 20% in mean anterior myocardial infarct size (IS), as determined by Cardiac Magnetic Resonance (cMR) imaging at 4-6 days post infarct in the Test Arm (cooling + PCI) compared to the Control Arm (PCI only). The absolute magnitude of a relative reduction of 20% depends on the mean IS in the control arm, which is assumed to be approximately 17 %LV. Therefore, the treatment effect of interest is an absolute difference of 3.5 %LV. Therefore, the treatment effect of interest is an absolute difference of 3.5 %LV.

The null hypothesis is that the mean IS in the Test Arm is equal to the mean IS in the Control Arm. The assumed standard deviation is 12 %LV and the final analysis will be conducted using a two-sided test at the alpha=0.044 level of significance (adjusted for the two interim analyses). Based on these assumptions, the required total sample to detect a mean difference of 3.5 %LV with 80% power is 384 subjects (192 subjects per group). Allowing for a potential dropout rate of 24%, the planned total sample size is 500 subjects (250 subjects per group).

$$H_0: \mu_T = \mu_C$$

$$H_A: \mu_T \neq \mu_C$$

Null hypothesis:

The null hypothesis is that the mean IS in the Test Arm is equal to the mean IS in the Control Arm.

Alternative hypothesis:

The mean %LV in the control arm is not equal to mean of control arm.

This 20% relative reduction is defined as absolute value 3.5 %LV and accounted for in our sample size calculation as treatment effect. This assumption is based on previous studies with anterior infarct size measured with cMR reporting between 17-20% absolute %LV in anterior infarct (**Tables 1 & 2**). Therefore, a relative reduction of 20% can vary depending on the mean infarct size of the control arm. Assuming a representative mean infarct size of ~17% in controls, we assume absolute difference of 3.5 %LV is equivalent to 20% mean anterior infarct size would be an adequate detection limit for effect.

COPY

Table 1: Clinical trials reporting anterior mean infarct size measured by cMR 4-6 days in PCI trials (Control Group Only) and calculated 20% relative reduction

Study name	Anterior n	Mean infarct size	Standard Deviation	20% relative reduction
APEX-AMI³⁷	60	16.6	10.7	3.3
LIPSIAABCIXIMAB³⁸	63	25.3	16.1	5.1
LIPSIA-STEMI³⁹	38	18	16.0	3.6
CRISP-AMI^{40*}	142	37.5	20.1	7.5
INFUSE-AMI⁴¹	172	17.3	10.2	3.5
RAPID-MI ICE¹	7	19.7	8.5	3.9
CHILL-MI³³	21	26.5	10.9	5.3
AMI EU PILOT	21	23.3	12.0	4

*>60% are large proximal infarcts

COPY

Table 2: Hypothermia trials using cMR measured infarct size as primary outcome

	RAPID-MI ICE (2009)	CHILL-MI (2013)	AMI EU Pilot (2017)	Pooled AMI EU Pilot, RAPID-MI-ICE, CHILL-MI
n (Control vs Cooled)	7 vs 5	21 vs 15	21 vs 19	49 vs 39
Control Mean LV%	19.7	26.5	23.3	24.5
20% reduction in infarct	3.94	5.3	4.7	4.9
Std Dev (control)	8.5	10.9	12.0	10.5
Std Dev (cooled)	6.5	9.3	10.3	11.0

The potential impact of variations in control infarct size and variability is presented in **Table 3**.

Table 3: Sample size estimates with alternative standard deviation and detection limit

Mean Difference in infarct size for detection (%)	Standard Deviation	Estimated Sample Size	Total Enrolment (with 20% drop-out)
3.0	9	288	360
3.0	10	355	444
3.0	11	430	534
3.0	12	506	636
3.5	9	212	264
3.5	10	260	330
3.5	11	314	396
3.5	12	374	468
4.0	9	162	204
4.0	10	200	252
4.0	11	240	300
4.0	12	286	360

The safety endpoint is a composite endpoint. In consideration regarding power of this study, expected incidence is based on a literature review of acute MI hypothermia trials that combined six studies: Dixon et al, COOL MI, ICE-IT, RAPID MI-ICE, CHILL-MI, VELOCITY¹¹ which resulted in a 30-day MACE rate of 6.6% in the Control patients and 7.5% in treatment patients. Previously, AMIHOT II trial defined 30-day MACE rate comprised of death, reinfarction, target vessel revascularization, and stroke used a non-inferiority hypothesis with a 6% equivalence delta and 7% in the Control patients¹².

The hypothesis for the primary safety endpoint is the following:

$$H_0: \pi_T \geq \pi_C + 6\%$$

$$H_A: \pi_T < \pi_C + 6\%$$

π_T and π_C are the underlying proportion of patients having a MACE event.

An enrolment of 500 would be able to demonstrate 91% power and 95% 1-sided significance with alpha=0.05. The safety endpoint will be considered to have been met if there is a high posterior probability of non-inferiority [i.e. $P(\pi_t < \pi_c + 6\%) > 95\%$]. With 20% dropout, the power becomes 86%.

6 General Considerations

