3.1 Study Objectives

This is a confirmatory trial to evaluate safety and effectiveness of therapeutic hypothermia using ZOLL Proteus IVTM System for patients with acute anterior MI in comparison with anterior MI patients who only undergo PCI. Efficacy is established by demonstrating a relative reduction of 20% in mean anterior myocardial infarct size (IS), as determined by Cardiac Magnetic Resonance (cMR) imaging at 4-6 days post infarct in the Test Arm (cooling + PCI) compared to the Control Arm (PCI only). Infarction Size (IS) is defined as % Left Ventricular Mass as measured by Cardiac Magnetic Resonance (cMR) imaging.

Infarct Size (IS) will be assessed by Cardiac Magnetic Resonance (cMR) at 4 – 6 days following the index procedure and is a measurement of “myocardial reperfusion injury” by a Core Lab.

The trial is considered to have met the primary efficacy endpoint if the Test Arm demonstrates a 20% relative reduction in mean infarct size (defined as a 3.5% absolute reduction) compared to the Control Arm.

Furthermore, safety will be evaluated throughout the trial on basis of non-inferiority, with 6% established as the margin of non-inferiority.

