4.1 General Study Design and Plan

A multicenter, prospective, interventional, randomized-controlled trial. Randomization will be in a 1:1 ratio, Test Arm (PCI + Cooling) or Control Arm (PCI alone). This is an unblinded trial with randomization using stratified by site using permuted blocks.

Subjects will be screened and randomized according to the following flow diagram:

[figure not shown]

Figure 1 Screening and Enrolment Flow

COPY

Follow-up after randomization (post-procedure, either Control with PCI only, or Test with PCI and Cooling) are described below:

[figure not shown]

Figure 2 All Patient Procedures

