6.7 Multiple Testing

For this trial, there is only one primary effectiveness outcome with two interim analyses. Overall significance value is preserved for interim analyses with established stopping rules preserving the overall type 1 error rate of alpha for <0.05.

For primary and secondary safety analyses, given the number of statistical tests, adjustment for multiplicity is considered counterproductive for considerations of safety as there is no control of the type I error for a single hypothesis. Tests will be conducted using one-sided test at alpha 0.05 level of significance.

All other analyses will be conducted using two-sided tests at the alpha=0.05 level of significance.

7 Summary of Study Data

[figure not shown]
Data will be sorted by treatment and centre and structured with columns for Test and Control. Descriptive and efficacy figures and tables will be produced for ITT and PP population. All

continuous variables will be summarised using the following descriptive statistics: n (non-missing sample size), mean, standard deviation, median, maximum and minimum. The frequency and percentages (based on the non-missing sample size) of observed levels will be reported for all categorical measures. In general, all tables will be annotated with population size relevant to the table/treatment, including any missing observations.

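### The stated power for the primary safety endpoint (91%, or 86% after dropout) does not follow from the SAP's own margin, alpha, sample size and cited MACE rates, and is too high

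*SAP*

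**What the plan says.** Section 3.1 sets the safety comparison as non-inferiority, "with 6% established as the margin of non-inferiority". Section 5 writes the hypotheses as H0: π_T ≥ π_C + 6% against H_A: π_T < π_C + 6%, where π is the proportion of patients with a MACE event.

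Section 5 then introduces the expected incidence for the power consideration. It rests on a literature review of six hypothermia trials, "which resulted in a 30-day MACE rate of 6.6% in the Control patients and 7.5% in treatment patients". The same paragraph mentions an earlier trial that "used a non-inferiority hypothesis with a 6% equivalence delta and 7% in the Control patients".

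The power statement follows: "An enrolment of 500 would be able to demonstrate 91% power and 95% 1-sided significance with alpha=0.05". Success is defined there as a posterior probability of non-inferiority above 95%. The paragraph closes with "With 20% dropout, the power becomes 86" per cent.

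Alpha and sidedness are confirmed for the safety analyses in Section 6.7: "Tests will be conducted using one-sided test at alpha 0.05 level of significance". The 500 subjects are split 250 and 250 (Section 5) under 1:1 randomisation (Section 4.1). Section 5 gives no formula, no prior and no explicit pair of design rates.

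**The concern.** MACE is an adverse outcome, so an expected excess in the test arm uses up part of the margin. With control at 6.6% and test at 7.5%, only 6.0 − 0.9 = 5.1 points remain. Power of 91% with 250 per arm looks too high for that distance, and it looks high even if the true rates are equal.

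This is the SAP's only power statement for the primary safety conclusion. It puts the chance of missing non-inferiority at 9% (14% after dropout) when the assumptions hold. If the true chance is much larger, a failed or marginal result would be read against the wrong expectation. Because the assumed rates are not given, a reader cannot check the figure.

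**Working it through.** **Inputs, all from the SAP.** Margin 0.06 (Sections 3.1 and 5). One-sided alpha 0.05, so z = 1.645 (Sections 5 and 6.7). n = 250 per arm, or 250 × 0.80 = 200 after 20% dropout (Section 5). Rates: control 6.6% and test 7.5%, or a 7% control rate (Section 5).

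**Formula** (unpooled normal approximation, p_T for test and p_C for control):

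SE = √[(p_T(1 − p_T) + p_C(1 − p_C)) / n]

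Power = Φ[(0.06 − (p_T − p_C)) / SE − 1.645]

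**Cited rates in their stated arms.** The variance sum is 0.075 × 0.925 + 0.066 × 0.934 = 0.1310.

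- n = 250: SE = 0.02289; 0.051 / 0.02289 = 2.228; Φ(2.228 − 1.645) = Φ(0.583) = 72.0%.
- n = 200: SE = 0.02560; 0.051 / 0.02560 = 1.993; Φ(0.348) = 63.6%.

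**Equal rates.** At 6.6% the variance sum is 0.1233. With n = 250, SE = 0.02221 and 0.06 / 0.02221 = 2.702, so power = Φ(1.057) = 85.5%. The other cells follow in the same way.

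| Control / test rate | 250 per arm | 200 per arm | Per arm needed for 91% |
|---|---|---|---|
| SAP as stated | 91% | 86% | – |
| 6.6% / 7.5% | 72.0% | 63.6% | 450 |
| 6.6% / 6.6% | 85.5% | 78.0% | 306 |
| 7% / 7% | 83.8% | 76.0% | 323 |

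The last column is the number of evaluable subjects per arm, n = (variance sum) × (1.645 + 1.341)² / (0.06 − (p_T − p_C))², where 1.341 is the normal quantile for 91%.

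**Does the method matter?** Exact enumeration of the SAP's posterior rule with flat Beta(1,1) priors gives, in the same row order, 71.7% / 62.8%, 85.1% / 76.9% and 83.4% / 75.2%. The flat prior is an assumption, since the SAP names none. Exact enumeration of the Wald test gives 72.5% / 63.8%, 85.8% / 78.1% and 84.0% / 76.0%. A Farrington-Manning test or a continuity correction lowers the first row further, to 69.2% / 60.5% and 65.8% / 56.1%. No standard method moves the cited rates toward 91%.

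**What would give the stated pair?** These settings come close:

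- Arms reversed (control 7.5%, test 6.6%): the distance becomes 0.069, and power is 91.5% / 85.3%. This contradicts the rates as Section 5 assigns them.
- Equal 7% rates at one-sided alpha 0.10: 91.1% / 85.8%. This contradicts the alpha in Sections 5 and 6.7.
- Equal rates at alpha 0.05 with lower incidence: 91% at 250 per arm needs a MACE rate of about 5.3%, and 86% at 200 per arm needs about 5.1%. Both are below every rate the SAP cites.

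Which of these was used, if any, cannot be told from the document.

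**The case against.** The strongest counter-argument is that the success rule is Bayesian and its prior is unspecified. An informative prior can reach the stated figures. With both true rates at 7% and a prior worth 50 patients per arm centred at 7%, exact enumeration gives 91.1% and 86.5%. With equal 6.6% rates and a prior worth 40 patients per arm, the result is the same pair. That shows the method is undetermined, but it does not support the SAP's figures. Nothing in the SAP points to an informative prior, and Sections 6.7 and 9 describe one-sided frequentist tests. The 50-patient prior would also raise the false-positive rate at 7% against 13% to about 10%, which conflicts with the stated alpha of 0.05.

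Second, Section 5 never says outright that 6.6% against 7.5% is the design alternative, and planning non-inferiority under equal rates is common. That is fair. The gap is then about 5 to 7 points with 500 subjects and 8 to 10 after dropout, so the 19 and 22 points are the upper end of a range. The gap does not close under either reading.

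Third, the sample size was set by the effectiveness endpoint, and the trial was suspended before full enrolment (revision history and Section 6.4). This stands and limits the weight of the point: no enrolment decision rested on the safety power. It does not make the figures right. This revision was edited for the suspension and still carries them, and with fewer subjects the achieved power is lower still.

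**Conclusion.** The concern holds. With the SAP's margin, alpha and sample size, no cited rate or pair of rates, kept in its stated arm, gives 91% and 86%. On the rates named as expected incidence, power is about 72% and 64%, which is 19 and 22 points below the stated figures. Under no true difference it is about 84% to 86% and 76% to 78%. The chance of missing non-inferiority is therefore about 15% to 28% with 500 subjects (stated: 9%) and 22% to 36% after 20% dropout (stated: 14%).

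These figures assume 1:1 allocation and either a standard one-sided test of the difference in proportions or the posterior rule with flat priors. They do not identify how the error arose. The point should be corrected, but it changes no analysis.

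**What to change.** In Section 5, state the assumed 30-day MACE rate in each arm, the alpha and the method, including the prior if the posterior rule was used. Replace 91% and 86% with the figures that follow from that choice. By the normal approximation these are:

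- about 72% and 64% for control 6.6% and test 7.5%;
- about 86% and 78% for 6.6% in both arms;
- about 84% and 76% for 7% in both arms.

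The cost is one or two sentences and a less favourable stated power. Enrolment, test, margin, analysis set and success rule stay as they are.

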6.1 Timing of Analyses

The final analysis will be performed after enrolment is considered complete and all cMR and follow-ups have been performed except for patients lost to follow-up—for lost-to-follow up patients, reason will be documented. For final analyses, data will be cleaned in compliance with Data Management Plan and the finalization and approval of SAP documents.

6.2 Analysis Populations

The Intention-to-Treat (ITT) analysis set will be used for primary efficacy statistical analyses and summaries. The ITT population includes subjects who have signed an informed consent and have been randomized to the Test Arm or the Control Arm of the trial. ITT subjects will be evaluated according to the group to which they were randomized.

The Per-Protocol (PP) analysis set will also be evaluated. The PP population includes those subjects who met all inclusion and exclusion criteria, were randomized to either the Test or Control arm, received the treatment to which they were randomized, and complied substantially with the treatment timeline and steps of this protocol without major protocol violations.

The Safety Analysis Set, which includes all ITT subjects, will be used to evaluate safety endpoints. For the safety analysis, subjects will be followed for all adverse events for 12 months post procedure. Additionally, all subjects in this set will be confirmed as followed for 12 months for the incidence of Adverse Events, Serious Adverse Events (SAEs), Death and Heart Failure (as assessed by NYHA and Kansas City Cardiomyopathy Questionnaire (KCCQ), as applicable).

6.3 Covariates and Subgroups

Subgroups to be evaluated for heterogeneity of infarct size using an interaction model with treatment variable and the following subgroup variable: age (<65 vs >65 years), BMI (<25 vs >=25), BMI (<30 vs >=30), sex, door to balloon time (<60 minutes, 60-90 minutes, >90 minutes), ischemic time (<4 hours vs >4 hours), post-TIMI flow (0-2 vs 3), temperature at PCI (<32°C, 32-35°C, >35°C). Wald test or t-test p-value will be reported for each group as appropriate depending on final linear regression model.

In order to evaluate clinical characteristics in association with infarct size, separate univariate models may be considered for exploratory analysis: ischemic time, country and/or center. Analysis of covariance models will be used. Evaluation for independence, normality, homoscedasticity, and linearity will be applied. Square root transformation will be used if assumption is violated. Beta coefficient, standard error, 95%CI, and p-values will be reported. From among the variables with individually significant associations, after selection of single covariates from among any collections of highly collinear covariates based on their univariate associations with infarct size, a multivariate model will be built using forward and backward stepwise variable selection, to determine the variables with independently significant associations with risk, using a criterion of $p \leq 0.05$.

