7.3 Demographic and Baseline Variables

Demographics and Baseline clinical characteristics: age, sex, height (cm), weight (kg), BMI, systolic blood pressure (mmHg), diastolic blood pressure (mmHg), heart rate (beats/min), respiration (breaths/min), tympanic temperature at baseline (degree Celcius), glucose (mmol/L), calcium (mmol/L), magnesium (mmol/L), creatinine (umol/L), alcohol usage(current/past), smoking history (current/past), and medical history: history of cardiovascular conditions, diabetes, hypertension, and dislipidemia.

Treatment parameters: door to randomization, door to balloon time, door to wire-crossing time, randomization to wire crossing, randomization to balloon, and total ischemic time.

The summary statistics will be produced in accordance with section 6.

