7.6 Treatment Compliance

Assessment of treatment compliance including submission of 4-6 day cMR for both Control and Test patients and availability of IS for analyses. For Test patients, compliance is additionally assessed as number of patients who are Cooled, assessed through the *Initiation of Cooling* CRF, which notes date and time of cooling initiation and the variable indicating “Initiation of Cooling – Not Done”. Other

measurements of compliance include the adherence to DAPT protocol, which is recorded in the Medications CRF.

The summary statistics will be produced in accordance with section 6.

Substantial protocol compliance for inclusion into Per-Protocol population is defined as the following:

- Received assigned treatment
 - Test subjects with no interrupted or problematic cooling
- cMR completed with available IS data within window (10 days)
- No repeat infarction prior to 4-6 day cMR

8 Efficacy Analyses

Efficacy variable IS (LV%) will be listed by subject within study centre. Data will be summarised by treatment group. N, Mean, Standard Deviation, Minimum and Maximum will summarise continuous efficacy variables. Plan in handling missing data for missing IS are documented in Section 6.

All assumptions for regression models will be assessed by viewing plots of the residual values. Transformation will be applied as appropriate as necessary for exploratory analysis adjusted by covariates including ischemic time.

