Association of infarct size with covariates	ITT and PP	Association with covariates including age, BMI, sex, pre-TIMI flow, post-TIMI flow, DTB, Ischemic time, and temperature at PCI	4-6 day	NA	p-value
NYHA classification at 12 months	ITT	NYHA Classification	12 months	Treatment	x (p%), p-value
KCCQ summary at 12 months	ITT	KCCQ overall summary score and KCCQ clinical summary score	12 months	Treatment	n, mean, SD, median, min, max, p-value

COPY

NT-proBNP summary at 12 months	ITT	NT-proBNP	12 months	Treatment	n, mean, SD, median, IQR, min, max, p-value
Clinical outcome summary (death, MI re-infarction, or TVR at 30 days)	Safety analysis set	MACE (Primary Safety)	30-days	Randomization	x (p%), p-value
Clinical components of mace summary	Safety analysis set	Additional Safety Endpoints	30 days	Randomization	x (p%), p-value
Subjects with serious adverse events summary within 30 days	Safety analysis set	All Serious Adverse Events	30 days	Randomization	x (p%), p-value
Subjects with non-serious adverse events summary within 30 days	Safety analysis set	All Non-Serious Adverse Events	30 days	Randomization	x (p%), p-value
Subjects with serious adverse events summary within 12 months	Safety analysis set	All Serious Adverse Events	12 months	Randomization	x (p%), p-value
Subjects with non-serious adverse events summary within 12 months	Safety analysis set	All Non-Serious Adverse Events	12 months	Randomization	x (p%), p-value
Subjects with serious adverse events of interest within 30 days	Safety analysis set	Serious adverse events of interest	30 days	Randomization	x (p%), p-value
Subjects with death and stent thrombosis within 12 months	Safety analysis set	Death and Stent Thrombosis	12 months	Randomization	x (p%), p-value
DAPT and Anti-Thrombotic Medication	ITT	DAPT and Anti-Thrombotic Medications used	Baseline	Randomization	x (p%), p-value

COPY

Listing of Listings

Title	Population	Display Variables	Time Point	Sort Variable
Subjects not cooled	ITT	Randomization, Subject ID, Reason for not cooling	Baseline	Randomization
Protocol Deviations	ITT	Reasons for deviation	Baseline, 4-6 day, 30 days, 12 months	Randomization, Subject ID
Device Deficiency	ITT	Device type, device disposition, deficiency description	Baseline	Randomization, Subject ID
Serious Adverse Events	ITT	Adverse Event Number, Adverse Event, Adverse event start date, Outcome, Procedure relatedness, Device relatedness	Baseline, 4-6 day, 30 days, 12 months	Randomization, Subject ID, AE number

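### The treatment-interaction subgroups in Section 6.3 and the exploratory adjustment in Section 8 use variables that cooling can change after randomisation, so these secondary results are not randomised comparisons

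*SAP*

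**What the plan says.** **Subgroups.** Section 6.3 opens: "Subgroups to be evaluated for heterogeneity of infarct size using an interaction model with treatment variable and the following subgroup variable". Its list includes "door to balloon time (<60 minutes, 60-90 minutes, >90 minutes), ischemic time (<4 hours vs >4 hours), post-TIMI flow (0-2 vs 3" and then "temperature at PCI (<32°C, 32-35°C, >35°C". A p-value is to be reported for each. This paragraph does not call the tests exploratory and gives no caution that some of the variables follow randomisation.

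**Covariates.** The second paragraph of 6.3 says "separate univariate models may be considered for exploratory analysis: ischemic time, country and/or center. Analysis of covariance models will be used". Section 8 says "Transformation will be applied as appropriate as necessary for exploratory analysis adjusted by covariates including ischemic time". The list of tables in Section 13 has an infarct-size association table, for ITT and PP, described as "Association with covariates including age, BMI, sex, pre-TIMI flow, post-TIMI flow, DTB, Ischemic time, and temperature at PCI".

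**Timing.** The Test-arm schedule in Section 4.4 puts initiation of cooling, with cold saline and catheter insertion, in the column before reperfusion. Section 7.3 lists the treatment parameters as "door to randomization, door to balloon time, door to wire-crossing time, randomization to wire crossing, randomization to balloon, and total ischemic time".

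**Primary test.** Section 8.1 specifies a two-sided t-test or Wilcoxon rank-sum test with no covariates. Section 6.2 assigns the primary efficacy analysis to the ITT set, by randomised group.

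**The concern.** A subgroup or adjustment variable keeps the protection of randomisation only if treatment cannot have influenced it. Here it can:

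- **Door-to-balloon and total ischemic time.** Section 7.3 derives intervals from randomisation to wire crossing and to balloon, so part of each time accrues after allocation, while only Test subjects are being cooled.
- **Post-TIMI flow.** It is a result of the procedure.
- **Temperature at PCI.** This is the clearest case. Cooling is meant to lower it, so its bands will tend to separate the arms rather than divide each arm into comparable parts.

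Section 2.1 names the duration of ischemia as a factor in infarct size. If delivering cooling prolongs ischemia, the larger infarct that results is part of what the cooling strategy does. Holding ischemic time fixed, by adjustment or by banding, takes out some or all of that cost and makes cooling look better than the strategy is.

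The stake is the reading of secondary output. Section 6.4 says the trial never completed enrolment, so readers may lean more than usual on subgroup and adjusted results.

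A separate drafting slip is in the same sentence of 6.3. Age is split below against above 65, and ischemic time below against above 4 hours, so the boundary values fall in no group. The BMI splits beside them include the boundary.

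**Working it through.** **1. The plan's own figure.** No stated figure bears directly on this point. The design figure shows what the primary comparison rests on (Section 5: difference 3.5 %LV, SD 12 %LV, two-sided alpha 0.044, power 80%):

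n per arm = 2 × (z₀.₉₇₈ + z₀.₈₀)² × SD² / difference² = 2 × (2.014 + 0.842)² × 144 / 12.25 ≈ 192, or 384 in total.

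This reproduces the SAP and is the formula for an unadjusted two-group comparison. Nothing below changes it.

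**2. What adjustment removes.** Suppose infarct size = constant + direct effect × arm + slope × ischemic time, and cooling adds a mean delay to ischemic time. Then:

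- total effect of the strategy = direct effect + slope × delay
- effect adjusted for ischemic time = direct effect
- amount removed = slope × delay

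The SAP gives neither a delay nor a slope, so both are assumptions:

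| Assumed delay | Assumed slope | Amount removed |
|---|---|---|
| 10 min | 1 %LV/h | 1 × 10/60 = 0.17 %LV |
| 20 min | 2 %LV/h | 2 × 20/60 = 0.67 %LV |
| 30 min | 4 %LV/h | 4 × 30/60 = 2.0 %LV |

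**3. Simulation, including the 4-hour subgroups.** From the SAP: 192 per arm, Control mean 17 %LV, SD 12 %LV. Assumed: Control ischemic time with mean 3.5 h and SD 1.2 h, plus the delays and slopes shown. There were 1,500 repetitions. The Monte Carlo error of the unadjusted mean is about 12 × √(2/192) / √1500 = 0.03 %LV, and somewhat more in the subgroups. Entries are Test minus Control in %LV; negative favours cooling.

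| Delay, slope | Direct effect | True total | Unadjusted | Adjusted for ischemic time | Under 4 h | Over 4 h |
|---|---|---|---|---|---|---|
| 0 min, 2 %LV/h | −3.5 | −3.50 | −3.48 | −3.49 | −3.53 | −3.40 |
| 20 min, 2 %LV/h | 0 | +0.67 | +0.70 | +0.04 | +0.31 | +0.24 |
| 20 min, 2 %LV/h | −3.5 | −2.83 | −2.87 | −3.54 | −3.26 | −3.33 |
| 20 min, 4 %LV/h | −3.5 | −2.17 | −2.17 | −3.51 | −2.94 | −3.11 |

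The unadjusted comparison recovers the total effect in every row. Adjustment returns the direct effect only. Splitting at 4 hours hides roughly half or more of the delay cost: in the second row (0.67 − 0.31)/0.67 = 54% and (0.67 − 0.24)/0.67 = 64%. With no delay, all the estimates agree.

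**4. Post-TIMI flow and temperature at PCI.** No arithmetic is needed. The first is observed after the procedure. The second is measured after cooling has begun in one arm only.

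**The case against.** A reader might infer that any harm from cooling delay is adjusted out of the trial's efficacy result. The SAP does not support that. The deciding test in Section 8.1 has no covariates, is run in the ITT set, and by Section 6.6 is not adjusted for centre either. Whatever a delay costs stays in it.

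Other parts of the defence also stand:

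- The models with ischemic time in Sections 6.3 and 8 are labelled exploratory, and those in 6.3 are optional.
- Only ischemic time is named for adjustment. Door-to-balloon time and post-TIMI flow appear as subgroup and association variables. The stepwise model in 6.3 looks for associations with infarct size and names no treatment term.
- The SAP nowhere says that cooling delays PCI. That possibility is inferred from the order of the Test-arm schedule.
- The amounts above follow wholly from assumed inputs. Quoting them as a share of the 3.5 %LV target would wrongly suggest that the primary effect is exposed.
- Section 13 already tabulates treatment times, angiographic findings and temperature at wire crossing by randomised arm, so a delay would be visible.

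What the defence does not reach is the first paragraph of 6.3. Its interaction tests are not labelled exploratory, Section 6.7 puts them at two-sided 0.05, and they use variables that treatment can alter. A table of times by arm shows a delay but does not repair a subgroup contrast built on those times.

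**Conclusion.** The point holds for the subgroup interaction tests in Section 6.3 and the exploratory adjusted analysis in Section 8, and for nothing beyond them. Those results lack the protection of randomisation because four of the variables used arise wholly or partly after allocation and can be changed by cooling. This follows from the SAP's own schedule and interval list and needs no assumption about the size of any delay.

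The direction of the distortion is conditional: if cooling delays reperfusion and longer ischemia enlarges the infarct, the conditioned results favour cooling. The size is illustrative only, 0.17 to 2.0 %LV in the adjusted estimate for assumed delays of 10 to 30 minutes and slopes of 1 to 4 %LV per hour, and zero without a delay.

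The primary test and sample size are unaffected. The gaps at exactly 65 years and exactly 4 hours are certain but minor. The change is worth making because it is cheap and alters planned inferential output.

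**What to change.** 1. Keep the primary test unadjusted, as Section 8.1 has it.
2. In Sections 6.3 and 8, replace door-to-balloon time and total ischemic time in the subgroup and covariate analyses with time from symptom onset to randomisation. Compute it from the recorded onset and randomisation times. Do not obtain it by subtracting randomisation-to-balloon from total ischemic time, because the SAP does not say whether ischemic time ends at wire crossing or at balloon.
3. Remove post-TIMI flow and temperature at PCI from the treatment-interaction tests.
4. Report door-to-balloon time, total ischemic time, post-TIMI flow and temperature at PCI descriptively by arm, stating that treatment may have affected them. Bring the Section 13 table list into line.
5. Make the bands exhaustive: age <65 against ≥65 years, and time <4 against ≥4 hours. The 4-hour cut will then apply to a shorter interval, so fewer subjects will fall in the upper band. The SAP should acknowledge this.

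The cost is SAP wording and one derived variable. The small downside is less direct comparability with publications that stratify by total ischemic time.
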